based on well-established assays used in both healthy human participants and patients with chronic pain⁹. All assays involve either innocuous (non-painful stimuli) or acute noxious stimuli (painful stimuli) that do not damage tissue. Time between different tests will be >5 min to allow the subject to rest. Timing of testing on experimental days will be 5 minutes and 30 minutes following the completion of exercise or 30 minutes of rest (for control subjects and for all subjects on day 6). For all testing days order will proceed in the following manner. Training and description of each measure is as follows:

Cutaneous mechanical sensitivity assay¹⁰: Enrolled participants will be asked to sit in a chair (chair provided with arm-rests). Assay involves determining the sensitivity threshold for innocuous cutaneous stimulation. Stimulation is provided with standard sensory evaluator filaments (see equipment section below for image of filament). These are small nylon filaments each apply a single force (ranging from 0.008gram to 1.0gram). Before the start of the first experimental trial, subjects will be allowed to feel and manipulate the filaments. Starting with the smallest filament (0.008g; below the sensory threshold for human detection), 5 trials will be directed at the subject's forearm. During testing, subject is asked to look away from their forearm/calf. Experimenter will ask "Can you feel this" while the experimenter applies the filament to the subject's forearm or calf. With each filament, the experimenter will apply the filament 3 times in the "positive" trials. For the other 2 trials, the experimenter will not apply the filament but ask the subject, "Can you feel this?" These 2 "negative" trials will be randomly inserted with the 3 "positive" trials and are designed to test for false responses. If a subject detects ≥ 2 of the positive trials and 0 negative trials for a filament, that force will be the subject's "mechanical sensory threshold." For a single filament, if the subject detects < 2 of the real trials and/or > 0 of the false trials, the experiment will start another round of 5 trials with the next biggest filament until the sensory threshold is reached. Typical testing time for each body part (forearm and calf) is about 5 minutes.

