Radiant heat sensitivity assay¹¹: Assay involves determining the sensitivity threshold for painful thermal stimulation. Stimulation is provided with a radiant heat device¹¹. This device uses a focused light beam to slowly heat a subject's skin. Before the start of the training/ experimental trials, subjects will be shown device and allowed to feel the stimulus with their hand. Subject will be asked to rest their forearm or calf on a room temperature glass plate. Using a mirror, the light source will be positioned under a marked area on the subject's forearm or calf. Subjects are told to raise their leg or arm when they feel the stimulus transition from "innocuous warmth or heat" to "painful heat." When the leg or arm is raised from the surface of the glass, the thermal stimulus automatically stops and the time since the beginning of the trial is recorded as "latency to respond." Each trial lasts for a maximum of 20 seconds. The device is set so that typical withdrawal thresholds occur at approximately 10 seconds into the trial. The temperature on the glass at this point is $\sim 47^{\circ}\text{C}$ (121°F). The maximum temperature of the trial at the 20 second cutoff time point is 50°C which is well below the temperature that causes tissue damage in humans. For each limb, two trials will be completed in two distinct marked areas to avoid re-testing at a single site. Total testing time (2 trials on forearm and 2 trials on calf) is < 5 minutes.

A second assay will be used to evaluate the quality and unpleasantness of thermal pain. Each subject will receive a constant 45°C stimulus. 45°C is a standard temperature that is the typical minimal stimulus necessary to feel thermal pain. Stimulus (3cm x5cm heating block) will be applied for 3 seconds. Immediately following stimulus, the subject will be asked to evaluate the intensity and unpleasantness of the pain. This is done with a standard 0-10 visual analog scale (VAS). On the "intensity scale", "0" is represented as "no pain" and "10" is represented as "the worst pain imaginable." On the "unpleasantness scale", "0" is represented as "not unpleasant" and "10" is represented as "the most unpleasant sensation imaginable."

Example instructions for intensity VAS – *“Please use the scale below to tell us how intense your pain is. Place an “X” on the scale that best describes the intensity of your pain.”*

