Mechanical pressure sensitivity assays^{10,12}: Assay involves determining the sensitivity threshold for painful pressure stimulation and then determining the quality and unpleasantness of that same pressure in a separate trial. Stimulation is provided with a standard clinical pressure algometer (see below instrument section). This device consists of a 0.5-2cm probe connected to a pressure meter. The probe is placed on the subject’s forearm or calf and pressure is gradually applied. Before the first training/experimental trial subjects will be allowed to apply the stimulus to themselves. During a trial, pressure will gradually be applied until the stimulus transitions from “innocuous pressure” to “painful pressure.” At this point, subject will say “stop” and the stimulus will be removed from the subject’s forearm/calf. When algometer is removed from the subject, the greatest pressure applied is automatically recorded in the device. This is the “pressure pain threshold” for the trial. 2 trials will be applied each to the forearm and calf in two distinct sites (on each limb) to avoid damage to a single area. After the pressure threshold has been determined for a subject, 1 additional trial on each limb will be applied (in a third testing site). In this trial, the subject will be asked to evaluate the intensity and unpleasantness of a pressure stimulus given for 3 seconds. This is done with a standard 0-10 visual analog scale (VAS). On the “intensity scale”, “0” is represented as “no pain” and “10” is represented as “the worst pain imaginable.” On the “unpleasantness scale”, “0” is represented as “not unpleasant” and “10” is represented as “the most unpleasant sensation imaginable.” During this trial, the experimenter will tell the subject that they are going to apply a painful stimulus to the subject and then ask the subject to evaluate that pain (on the two VASs). The exact stimulus will be matched to the subject’s pain threshold determined during the baseline trials (e.g. if baseline trials for forearm indicated a pressure threshold of 50 N then subject will be asked to evaluate the pain of that stimulus). During subsequent testing days (days 1, 3, 5, 6), the pressure pain threshold will be re-measured to determine if there is a change from baseline. For the intensity/unpleasantness testing, subjects will be tested on experimental days 1, 3, 5, 6 at their original baseline pressure threshold (from day 0) AND the threshold determined on each individual day. This will allow an analysis of change from baseline and pain at threshold for each experimental day.

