The collection of data has been described in detail under "Procedures". The primary outcome is a change in Quantitative Sensory Testing. This includes a series (8) of Quantitative Sensory Tests measured at baseline and at the completion of the 1-week intervention period. These tests are measured at two sites (calf and forearm). Significant differences between groups for 7 of the tests (per body site) will be identified using a one-way ANOVA comparing percent change from baseline (post-test (i.e. day 6)/baseline test (i.e. day 0)). Given the number of statistical tests that will be required for the primary outcome measurements, $p < 0.01$ will be utilized for each body site. An additional test for mechanical sensitivity will be measured at each site using a rank sum test at $p < 0.05$.

The secondary outcomes for this study include (1) HR during exercise, (2) Borg RPE before and after exercise and (3) testing "acute" effects of exercise on QST testing. HR during exercise and Borg RPE are measured to make sure that exercise causes a change in HR and/or perceived exertion. HR and Borg RPE data will be analyzed using percent change from start of exercise (post-exercise/pre-exercise) with two-way ANOVA for 3 treatment groups (3-day, 5-day, 10 day) across time (day 1, 3, 5) with an adjusted p value of $p < 0.03$. Control group will not be included in that analysis as HR was not measured on the control days and perceived exertion is at "0" on all days. For acute effects of exercise, participants were given 8 QST tests (on each forearm and calf) 5 min and 30 min after each exercise (or control session) on days 1, 3, and 5. Significant differences between groups for these tests (per body site) will be identified using a two-way MANOVA comparing percent change from baseline (post-exercise/baseline test (i.e. day 0)) across the three days (day 1, day 3, day 5) and at the 5 min and 30 min time QST measuring point. Given the number of statistical tests ($n=8$) that will be required for the QST secondary outcome measurements, $p < 0.01$ will be utilized for each body site.

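### The pressure rating is introduced as a painful stimulus, but the re-applied Day 0 pressure may not be painful after exercise; neutral wording would remove a possible dilution of the change in rating

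*Combined protocol and SAP*

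**What the plan says.** The procedure is in section 3, under the mechanical pressure sensitivity assays. The pressure threshold is the point at which gradually rising pressure turns from innocuous to painful. After it is found, a further trial at a third site applies pressure for 3 seconds, and the subject rates intensity and unpleasantness. In that trial "the experimenter will tell the subject that they are going to apply a painful stimulus to the subject", and the subject then rates the announced pain on two scales. The stimulus is matched to the "pain threshold determined during the baseline trials". Zero is an available mark: it means no pain on the intensity scale and not unpleasant on the other.

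On Days 1, 3, 5 and 6 "the pressure pain threshold will be re-measured to determine if there is a change from baseline". The ratings on those days are taken "at their original baseline pressure threshold (from day 0) AND the threshold determined on each individual day". No different lead-in is given for later days, for any arm, or for one pressure as against the other.

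For the 45°C heat rating the section describes no announcement: "Immediately following stimulus, the subject will be asked to evaluate the intensity and unpleasantness of the pain". Section 8 compares the arms on seven tests per body site by "one-way ANOVA comparing percent change from baseline (post-test (i.e. day 6)/baseline test (i.e. day 0", at p < 0.01.

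**The concern.** At Day 0 the announcement is true for everyone, because the pressure is the subject's own pain threshold. On a later day it is still true where the threshold has not moved. Where the threshold has risen, the re-applied Day 0 pressure lies below the current threshold and may not be painful, yet the subject has just been told that it will be. The wording is the same for all, but its accuracy then depends on whether the subject has responded, which is what the trial sets out to measure.

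The outcome is a subjective mark on a scale. A subject told to expect pain, and asked to evaluate that pain, may be reluctant to mark 0 or close to it. If so, the Day 6/Day 0 ratio in responders is held up and the exercise-control contrast shrinks. Analysis could not correct this afterwards, because the effect of the wording is not measured.

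**Working it through.** **Plan's own figure.** The documents give no figure for the effect of the announcement, so there is none to reproduce. Everything below that is not marked as from the plan is an assumption.

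**Inputs from the plan.** Outcome: Day 6 rating divided by Day 0 rating. Test: one-way ANOVA over four arms at 0.01 (section 8). Minimum of 10 subjects per arm (section 5).

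**Assumed inputs.** True ratings x0 on Day 0 and x6 on Day 6 in a responder, no change in control (ratio 1), and a script effect of b points. The true contrast is 1 − x6/x0.

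**(a) Equal additive shift on both days, all arms.** The contrast becomes (x0 − x6)/(x0 + b), so the share kept is x0/(x0 + b), whatever x6 is. For x0 = 3, x6 = 2:

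| b | Contrast | Share kept |
|---|---|---|
| 0 | 1/3 = 0.333 | 100% |
| 0.25 | 1/3.25 = 0.308 | 92% |
| 0.5 | 1/3.5 = 0.286 | 86% |
| 1.0 | 1/4 = 0.250 | 75% |
| 1.5 | 1/4.5 = 0.222 | 67% |

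The difference in raw points stays at 1.

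**(b) Proportional shift.** Both ratings are multiplied by the same factor, which cancels. The share kept is 100%. A proportional effect also cannot lift a true 0.

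**(c) Floor.** Only the later, non-painful stimulus is affected: a true fall from 3 to 0 is scored as 3 to b. The share kept is 1 − b/3, which is 92% for b = 0.25, 83% for b = 0.5 and 67% for b = 1.

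The loss at x0 = 3 therefore runs from none in (b) to between 8% and 33% in (a) and (c). It grows as the Day 0 rating falls: at x0 = 2, the shifts in (a) cost 1 − 2/2.25 = 11% to 1 − 2/3.5 = 43%.

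**Power of the planned ANOVA.** Simulated with 10 per arm, alpha 0.01, 20,000 runs, Day 0 mean 3 (SD 1), change SD 0.8, and a 1-point fall in all three exercise arms:

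| Script effect | b = 0.5 | b = 1.0 |
|---|---|---|
| Additive | 0.48 | 0.51 |
| Proportional | 0.44 | 0.44 |
| Floor | 0.47 | 0.38 |

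Without a script effect, power is about 0.44. Power can rise while the contrast shrinks, because the spread of the ratio shrinks faster. Type I error stayed at about 0.01 or below throughout.

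The answer depends on how low the ratings are. With Day 0 mean 1.5 (SD 0.5), change SD 0.5 and the same 1-point fall, lifting only true zeros to 0.5 or 1.0 cuts the contrast from 0.65 to 0.53 or 0.41, and power from 0.94 to 0.84 or 0.32.

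**The case against.** The strongest reply is that the direction and size of any effect are conjecture. The same words are used at Day 0 and in every arm, at a pressure that only just hurts, so the Day 0 rating may be lifted as well. A uniform shift leaves the raw-point contrast alone, and a proportional one leaves the ratio alone. This stands. A reader might infer that the announcement pushes ratings up and masks the analgesia, but the documents do not support that as a statement of fact.

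A reader might also infer that a quarter to a half of the effect is lost. That follows from a Day 0 rating of 2, a true Day 6 rating of 0 and a script effect of 0.5 or 1.0 on the responder's Day 6 mark alone (0.5/2 = 0.25, 1/2 = 0.50). Adding the same amounts to both days gives 0.5/2.5 = 0.20 and 1/3 = 0.33 instead. Either way it describes one complete responder, not a group mean.

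Four further limits stand:
- A higher threshold under rising pressure does not prove that a 3-second stimulus at another site is painless.
- Pressure that does not hurt can still be unpleasant, so the argument from a true zero applies to intensity only.
- Section 8 counts eight tests without listing them, and does not say which of the two pressures supplies the primary rating. It cannot be asserted that four primary measures are affected. The same-day threshold pressure is painful by definition.
- Use of the announcement on later days is the natural reading but is not written out.

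Two mitigations are real but partial: zero is an explicit anchor, and subjects may try every assay before full enrolment. The filament assay's blank trials "are designed to test for false responses" in a yes/no task, so they are no precedent for a graded rating.

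The reply does not show that the label stays accurate. Identical words are not an identical condition when they are true for some subjects and possibly false for others.

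**Conclusion.** The concern holds as a risk of dilution. The announcement is a leading instruction before a subjective rating, and it can be untrue for subjects whose threshold has risen. Only the ratings made at the Day 0 pressure are exposed, intensity most clearly.

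The size is unknown. The range of roughly 8% to 33% of the ratio contrast assumes a Day 0 rating near 3 and an additive or floor effect. It is nil for a proportional effect and larger if Day 0 ratings are lower. Loss of power does not follow from the text, since power moved in both directions under the assumed values. The case for a change rests on its low cost and on the fact that the effect cannot be removed in analysis.

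**What to change.** Replace the announcement with neutral wording, identical in all arms, on all days including Day 0, and at both pressures so that the subject cannot tell the two trials apart. For example: 'I am going to apply pressure for 3 seconds. Please mark any pain you feel, and mark 0 if it is not painful.' Give the unpleasantness scale a matching neutral lead-in, and state in section 3 that this script applies to every rating trial.

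The cost is script wording and a short briefing of testers. No stimulus, visit or analysis changes, and consent still tells subjects that testing may be painful. The wording should be settled before a subject's Day 0 session, so that both parts of the Day 6/Day 0 ratio are collected under the same script.

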
Procedures: Following the screening and training session, subjects will be randomized to one of four conditions (Control, Low Frequency of Exercise, Moderate Frequency of Exercise, and High Frequency of Exercise) and scheduled for their exercise and data collection sessions (Figure 1). Subjects in the control group will be scheduled for three experimental sessions within a five-day period: Days 1, 3, and 5. Control subjects will complete all of the physical and sensory/pain tests following a 30-minute period of rest (no physical activity) on each of these days. These subjects will be set up in a private room with various reading materials during this time period. Subjects in the low frequency of exercise group will be scheduled for three exercise sessions within a five-day period: Days 1, 3, and 5. Subjects in the moderate frequency exercise group will be scheduled for five exercise sessions within a five-day period: Days 1-5. Subjects in the high frequency exercise group will be scheduled for ten exercise sessions within a five-day period: Days 1-5. For all subjects, physical and sensory/pain measures will be taken on exercise days 1, 3, and 5, 5 and 30 minutes after exercise, and also on Day 6 (no exercise).

Exercise Session

Subjects will arrive at the Health Science Exercise Physiology Lab on their scheduled exercise days. Sessions will be scheduled at the same approximate time each day to control for factors that may influence exercise performance. At the initiation of each exercise session, HR measures will be taken. At the initiation of the session on days 1, 3, and 5, pain measurement will be made using the 3 assays described in detail above. For each assay, pain will be individually defined on a 0-10 visual analog scale (VAS), a common scale used in human pain testing¹³. Each assay is safe and produces only mild escapable acute (<1 min) pain. Pain measurements will be completed on both the calf and volar non-dominant forearm for each subject. On days 2 and 4 for subjects in the moderate frequency and high frequency of exercise group, sensory and pain measures are not collected.

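### Read literally, section 3 gives exercisers a pre-session test battery that controls do not get; other text omits that battery, and the high group's tested session is not named

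*Combined protocol and SAP*

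**What the plan says.** All references are to the combined protocol and SAP.

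- **Exercisers.** The Exercise Session part of section 3 concerns people who come in to exercise: "Subjects will arrive at the Health Science Exercise Physiology Lab on their scheduled exercise days". It places a battery before the walk ("At the initiation of the session on days 1, 3, and 5, pain measurement will be made using the 3 assays") and, at its end, further pain measures 5 and 30 minutes after the walk.
- **Controls.** The Procedures part of section 3 states: "Control subjects will complete all of the physical and sensory/pain tests following a 30-minute period of rest (no physical activity) on each of these days". No test before the rest period is described.
- **Statements covering every arm.** The general timing statement in section 3 reads "Timing of testing on experimental days will be 5 minutes and 30 minutes following the completion of exercise or 30 minutes of rest". Procedures adds "For all subjects, physical and sensory/pain measures will be taken on exercise days 1, 3, and 5, 5 and 30 minutes after exercise". Neither mentions a test before the session.
- **High group.** "Subjects in the high frequency exercise group will be scheduled for ten exercise sessions within a five-day period: Days 1-5". No sensory or pain tests are done on Days 2 and 4. Nothing says whether one or both sessions on a testing day are tested.
- **Analysis (section 8).** The primary analysis is a one-way ANOVA of Day 6 relative to Day 0 at p < 0.01, for seven tests per body site, with a rank sum test for the eighth. The acute analysis uses tests at "5 min and 30 min after each exercise (or control session) on days 1, 3, and 5", again relative to Day 0. HR and RPE are analysed by day, without naming the session that supplies the high group's values.

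**The concern.** Repeated sensory and pain testing can itself change responses, through habituation or sensitisation. If one arm is tested more often than another before Day 6, a between-arm difference at Day 6 mixes the effect of exercise with the effect of testing. A one-way ANOVA on the Day 6 to Day 0 ratio has no term that could separate them.

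The acute analysis has the same problem within the day. On the literal text, an exerciser's 5-minute test is the second battery of that day, while a control's is the first. For the high group, a post-exercise value could follow one walk or two. Two staff members could read the text differently and run different schedules.

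**Working it through.** **Inputs.** The plan states no battery count, so there is no figure to reproduce. The counts below come from the text of section 3 and section 8, with these conventions:

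- Testing days within the intervention week: 1, 3 and 5.
- Post-session batteries per tested session: 2 (5 and 30 minutes). Section 8 gives controls both time points.
- Pre-session batteries per tested session: 1 on the literal Exercise Session text, 0 on the statements covering every arm.
- High group: 10 sessions / 5 days = 2 a day on average, taken here as 2 on each testing day.
- Day 0 and Day 6: counted as one battery each. They are shared by all arms, so they do not affect differences.

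**Counts on Days 1-5.**

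- Control: 3 x 2 = 6.
- Low and moderate: 3 x (1 + 2) = 9 literally, or 3 x 2 = 6 if there is no pre-session battery.
- High, one session tested: the same as low and moderate.
- High, both sessions tested: 3 x (1 + 4) = 15 if the pre-session battery is given once a day; 3 x (2 + 4) = 18 if given before both; 3 x 4 = 12 if there is none.

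| Reading | Control / low / moderate / high, Days 1-5 | Adding Days 0 and 6 |
|---|---|---|
| Post-session only, one session a day | 6 / 6 / 6 / 6 | 8 / 8 / 8 / 8 |
| Literal section 3, one session a day | 6 / 9 / 9 / 9 | 8 / 11 / 11 / 11 |
| Post-session only, both high sessions | 6 / 6 / 6 / 12 | 8 / 8 / 8 / 14 |
| Literal, pre once a day, post after both | 6 / 9 / 9 / 15 | 8 / 11 / 11 / 17 |
| Literal, pre and post at both | 6 / 9 / 9 / 18 | 8 / 11 / 11 / 20 |

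Low and moderate are equal in every row.

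**Acute analysis, literal reading, one session a day.** Batteries already received before the 5-minute test, counting Day 0:

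- Exercisers: 2, 5 and 8 on Days 1, 3 and 5.
- Controls: 1, 3 and 5.

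The gap is 1, 2 and 3, so it grows over the same days that the analysis compares.

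**Illustration for the primary ANOVA.** The documents give no size for a testing effect. Assume that each battery shifts the Day 6 outcome by s SD, equally in all arms, and that exercise has no effect. The arm means are m = s x batteries, f = sqrt(mean of (m - mean m)^2), and the noncentrality is N f^2 with 3 and N - 4 degrees of freedom. For 6/9/9/9 and s = 0.10, the means are 0.6, 0.9, 0.9 and 0.9, so f = 0.130. With 15 per arm (the recruitment goal, N = 60) the noncentrality is 60 x 0.130^2 = 1.01. Rejection rates per test at a nominal 0.01, with 15 per arm:

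| Batteries, Days 1-5 | s = 0.02 | s = 0.05 | s = 0.10 |
|---|---|---|---|
| 6/6/6/6 | 0.010 | 0.010 | 0.010 |
| 6/9/9/9 | 0.011 | 0.014 | 0.031 |
| 6/6/6/12 | 0.013 | 0.031 | 0.145 |
| 6/9/9/15 | 0.014 | 0.047 | 0.273 |
| 6/9/9/18 | 0.019 | 0.099 | 0.598 |

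With 10 per arm and s = 0.10, the last four rows become 0.022, 0.080, 0.145 and 0.346.

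**The case against.** Only one sentence mentions a pre-session battery. The general timing statement, the sentence covering all subjects, the end of the Exercise Session text and section 8 list only the tests at 5 and 30 minutes. On that reading, with one tested session a day, the arms are equal at 6. Figure 1, to which Procedures refers for scheduling, is not shown and may be clearer. The filament assay is innocuous, the plan describes the pain as mild and brief, and the heat and pressure threshold trials use distinct sites.

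Much of this stands, and it limits the size of the point. It does not remove it. Leaving a battery out of a list does not cancel an explicit instruction to perform it, and the control text puts all tests after the rest. Section 8 also notes that HR was not measured on control days, although Exercise Session takes HR at the start of every session. That suggests start-of-session measures were not meant for controls.

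A reader might go further and infer that testing rises with dose across the arms, or that the high group has 2.5 times the control exposure (20 against 8). The documents do not support either. Low and moderate are equal in every reading, and high differs from them only if both daily sessions are tested. The figure of 20 needs pre- and post-session batteries at both sessions. The singular wording for the pre-session test, set against HR at each session, points the other way. So does an acute analysis with three days and two time points and no factor for a second session.

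**Conclusion.** The documents contradict themselves on whether a pre-session battery exists. The literal text of section 3 gives exercisers 9 batteries on Days 1-5 and controls 6, which is 50% more. This affects the control-versus-exercise contrast. It affects high against low and moderate only if both daily sessions are tested, and it does not affect low against moderate. Neither the primary nor the acute analysis can separate test exposure from exercise.

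The size and direction of any bias are unknown. Under the assumed shifts of 0.02 to 0.10 SD per battery, with one session a day tested and 15 per arm, the false-positive rate per test is 0.011 to 0.031 instead of 0.01, which is modest. The large inflations appear only with double testing in the high group. These rates illustrate a linear effect, equal per battery in all arms; they are not estimates.

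**What to change.** Reconcile the general timing statement, Procedures and Exercise Session in section 3, and section 8, into one battery schedule that is identical in all four arms.

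- **Simplest option: drop the pre-session battery in every arm.** Section 8 expresses all QST changes relative to Day 0, so no planned analysis loses anything. The only loss is an unplanned same-day reference value.
- **Alternative: also give it to controls, before their rest.** This equalises exposure but is not trivial. By section 3's own timings, filaments take about 5 minutes at each of two sites (2 x 5 = 10), and two gaps between the three assays take more than 5 minutes each (more than 10). That is more than 20 minutes before heat and pressure are added, on each of three visits.

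In either case, state that one session per testing day is tested in the high group, name it, and take the HR and RPE values for section 8 from the same session. With equal counts (6/6/6/6 or 9/9/9/9), a per-battery effect that is the same in all arms cancels and the ANOVA keeps its nominal 0.01. The cost is a few sentences in sections 3 and 8.

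If testing has already been done, report the number of batteries each arm received and which high-dose session was tested, and acknowledge any difference as a limitation.
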